In 2017, the National Cancer Institute's (NCI) Center to Reduce Cancer Health Disparities (CRCHD) is launching a nationwide CRC initiative called *Screen to Save*. The goal is to increase CRC screening rates among 50-75 year olds, especially from racially and ethnically diverse populations, people living in rural areas, and other populations that have historically had lower CRC screening rates than the general population. The initiative will involve up to 49 sites—including NCCC—that have received NCI/CRCHD funding to support Community Health Educators. Community Health Educators are expected to disseminate CRC information, education, and screening options in their communities, with the goal of increasing awareness, knowledge, and positive behavior change. Efforts will include educational social media messages; distribution of handouts, brochures, and other small media; and community-based outreach events. This last effort—the community-based outreach events—will take place at locations such as health fairs, festivals, and community-based organizations and will include data collection efforts.

Several public health interventions have been recommended by The Community Preventive Services Task Force to increase colorectal cancer screenings. Some of these interventions include client reminders, small media, one-on-one education, and the reduction of structural barriers. However, The Community Preventive Services Task Force has found insufficient evidence to determine the effectiveness of group education (e.g., lectures, interactive presentations using inflatable colons) in increasing colorectal cancer screening. Yet, some smaller studies have suggested that group education for colorectal cancer can be effective. As such,

NCI/CRCHD has asked its 49 funded sites to conduct group education activities/outreach events in their catchment areas and collect evaluation data to understand if knowledge and behavioral intention changed as a result of the education. This effort will contribute to the evidence-base for group education and will help NCI/CRCHD with future planning of national initiatives.

2. Objectives and Hypotheses

The purpose of this project is to: (1) contribute to a nation-wide initiative to educate the public about colorectal cancer and colorectal cancer screening, (2) evaluate the effectiveness of group education about colorectal cancer in changing knowledge and behavioral intention.

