- 2) Complete a pre-test that will be administered via paper/pencil at the group education activity/event. The participant will complete the pre-test immediately before being exposed to the educational content about CRC. The pre-test includes information about demographics, health insurance/health care coverage, prior CRC screening, family health history, and CRC knowledge (see attached).
- 3) Participate in a colorectal cancer education activity.
- 4) Complete a post-test that will be administered via paper/pencil at the group education activity/event. The participant will complete the post-test immediately after being exposed to the educational content about

CRC. The post-test includes information about CRC knowledge and behavioral intentions related to CRC (see attached).

Please note that the NCI toolkit included with this application indicates that subjects will be followed over three months. That is not the case, so identifying information will not be collected for subjects

Confidentiality:

Participant responses will be linked using unique identifiers that NCI/CRCHD (or its independent contractor) will be providing. Each participant will be assigned a 7-digit unique identification number. The first two digits identify the participating National Outreach Network (NON) site (i.e., that the data is coming from Dartmouth/NCCC); the next two digits identify the geographical region in which the NON site is located (i.e., that Dartmouth/NCCC is in CRCHD's Region 1 North); the last 3 digits will be sequentially assigned to participants. NCI/CRCHD (or its independent contractor) will provide NCCC with pre-printed labels containing unique identification numbers, 10 labels per unique identifier. The pre-printed label will be applied to each of the hard-copy forms that the participant is required to complete, which will include the pre- and post- tests.

When participants review the information sheet with a CITI-trained research team member, they will then be handed a card with a barcode/unique identifier on it. They will show the card to other research team members throughout the event to match to their pre-test and their post-test.

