Because NCI/CRCHD wants a sample size of approximately 4,000 individuals nationally, each site (including NCCC) has been asked to get 100 people 50-74 years old to complete both surveys and the education. As such, our target recruitment size is 100-150 people, with the goal of 100 completing both surveys and the education. To minimize attrition and encourage people to stay at the event to complete both surveys, we will provide a \$10 gift card to people who complete the pre-test, education, and post-test.

4. Analysis

Describe any qualitative tests and measures as well as quantitative methods:

NCI/CRCHD's independent contractor provided our raw, de-identified data back to us. We would like to use the data to evaluate the program's effectiveness related to changes in knowledge and behavioral intention from pre- to post-intervention. We will also assess whether there are any differences in changes for audience subgroups (e.g., men/women, age groups, participants at different events).

Please see the attached document from NCI/CRCHD entitled *Screen to Save Data Collection Storage and Security* for additional information about analysis.

5. Study Progress Monitoring

Note: appropriate monitoring may include periodic assessment of the following:

- data quality
- timelines
- recruitment and enrollment

Provide a description of the methods which will be used to determine the progress of the study, including periodic assessments of data quality, timelines, recruitment, and enrollment as appropriate:

Recruitment:

The project recruitment will start in March 2017 and end by September 2017. To reach our enrollment goal of 100-150 people, we expect to conduct a minimum of two outreach events that include data collection/recruitment. After the first two outreach events, we will determine how many additional outreach events with recruitment are needed to have 100 people finish the pre-test, education, and post-test. If needed, we will schedule additional outreach events and coordinate with partner organizations in the community.

Timeline:

NCI/CRCHD has provided an ideal timeline (see page 12 of *NCI Colorectal Cancer Outreach and Screening Initiative Toolkit*) to all participating cancer centers, including NCCC. We will do our best to follow NCI/CRCHD's proposed timeline by implementing electronic reminders for the research team to review progress. We will also have periodic research team meetings to ensure the project is progressing appropriately.

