STATISTICAL ANALYSIS PLAN WITH RESULTS

Screen to Save: A Colorectal Cancer Educational Intervention

NCT03907579

Date: July 8, 2020

ANALYSIS - BACKGROUND

For the Screen2Save intervention, subjects first take a survey, participate in the intervention and then take a final survey. The questions are the same on both surveys. All analysis was done using Stata/SE 15.1.

DID THE INTERVENTION CHANGE THE SURVEY RESULTS?

We are most interested in whether the subjects scored better (had more correct answers) in the post survey than the pre survey. Thus, for analysis purposes, each question was coded as a dichotomous Correct or Not Correct. If a subject did not submit a response for the question, it was coded as Not Correct (we may want to revisit this).

In order to test whether there was a difference in the Correct responses in the pre and post tests, McNemar's Test was used.

The McNemar test is a non-parametric test for paired nominal data. It's used when you are interested in finding a change in proportion for the paired data. For example, you could use this test to analyze retrospective case-control studies, where each treatment is paired with a control. It could also be used to analyze an experiment where two treatments are given to matched pairs. This test is sometimes referred to as McNemar's Chi-Square test because the test statistic has a chi-square distribution. (<https://www.statisticshowto.com/mcnemar-test/>)

When sample sizes are small, the chi-squared value may not be well-approximated by the chi-squared distribution. The exact p-value can be computed.

Thus, for each pair of pre and post questions, McNemar's Test was performed and both the Chi² and the exact P-value are shown. If the p-value is significant (<0.05), then the null hypothesis (H₀ = the number of correct responses on the pre survey are the same as on the post survey) can be rejected.

HOW DID THE SURVEY RESPONSE CHANGE?

Although the primary interest is whether the intervention increased knowledge about Colorectal cancer and screening, understanding what the specific responses were to the surveys is also of interest. CrossTab tables help to both quantify and visualize the relationship between the Pre and Post responses. The Pre responses are shown in the rows while the Post responses are in the columns. The light green to dark blue color gradient highlights the low to high number of responses for each category.

Did the intervention increase the number of correct answers?

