In order to look at the overall impact of the intervention, the number of correct responses was tabulated for each participant pre and post intervention. This data is shown in a CrossTab table. As with the individual questions, no response/null answers were coded as incorrect. In order to test of the number of correct responses was significantly different pre and post intervention, the Wilcoxon Signed-Rank Test was used. This is the non-parametric (i.e. not normally distributed) equivalent of a paired t-test.

SURVEY RESPONSES – WITH McNEMAR'S CHI2 TEST STATISTIC AND EXACT P-VALUE AS WELL AS CROSSTAB

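### The SAP's post-test total score is 69 correct answers short of its own item tables, so the reported mean gain is 0.76 where the items give 1.45; as a minor point, the pre-to-post change in intention planned in Section 4 has no baseline

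*Protocol*

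**What the plan says.** **Knowledge total.** In the SAP's section on whether correct answers increased, "the number of correct responses was tabulated for each participant pre and post intervention", and the two totals are compared with the Wilcoxon signed-rank test. The scoring rule is the one used for single items: "As with the individual questions, no response/null answers were coded as incorrect". The SAP then reports a mean of 10.78 before and 11.54 after, a maximum of 14 before and 13 after, z = -3.861, and a table of post-minus-pre changes.

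**Subgroups.** Protocol Section 4 adds: "We will also assess whether there are any differences in changes for audience subgroups". The SAP shows no such comparison and gives no reason.

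**Intention.** The second purpose in Protocol Section 2 is to "evaluate the effectiveness of group education about colorectal cancer in changing knowledge and behavioral intention". Section 4 is where a before-and-after comparison is spelled out: the team would like to evaluate "effectiveness related to changes in knowledge and behavioral intention from pre- to post-intervention". On the instruments, Protocol Section 3 says: "The pre-test includes information about demographics, health insurance/health care coverage, prior CRC screening, family health history, and CRC knowledge". It lists behavioral intentions for the post-test only. The SAP's Intent section says these questions were asked once and so were not analysed. Its background section nevertheless says of the pre and post forms: "The questions are the same on both surveys".

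**The concern.** With the same items, participants and rule for blanks, a total score must equal the sum of its items, so the mean total times 100 must equal the summed item counts. That holds for the pre-test and fails for the post-test.

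The total is the SAP's only overall measure of whether knowledge rose. If the post-test total is scored over fewer items than the pre-test total, the difference mixes learning with a scoring gap. The reported gain, the signed-rank test, the cross-tabulation and the count of people who got worse all inherit it. Any subgroup comparison built on the same score would inherit it too.

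The intention point is smaller. One of the two outcomes in the protocol's evaluation purpose has no baseline, and a reader setting Section 4 beside the SAP finds the reason but no statement that a planned analysis was dropped.

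**Working it through.** **Step 1. Reproduce the SAP's reported totals.** Margins of the total-score cross-tabulation, with the category printed as Yes taken as 1 (the minimum in the summary statistics):

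- Pre: 1×1 + 4×1 + 6×2 + 7×3 + 8×6 + 9×6 + 10×22 + 11×16 + 12×24 + 13×12 + 14×7 = 1078, mean 10.78, as reported.
- Post: 1×1 + 8×4 + 9×4 + 10×11 + 11×17 + 12×31 + 13×32 = 1154, mean 11.54, as reported.
- Change table: -4×1 - 2×5 - 1×19 + 0×20 + 1×29 + 2×9 + 3×11 + 4×2 + 5×3 + 6×1 = 76 = 1154 - 1078, mean gain 0.76.

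The SAP's total-score outputs therefore agree with each other.

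**Step 2. Sum the item tables.** Correct counts are the printed margins of each question's table. The last column is (net change)² / printed McNemar chi2, which should return the whole number of discordant pairs.

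| Item | Pre | Post | Net | Printed chi2 | Net²/chi2 |
|---|---|---|---|---|---|
| 1 | 69 | 69 | 0 | 0.00 | n/a |
| 2 | 66 | 74 | 8 | 3.20 | 20.00 |
| 3 | 44 | 72 | 28 | 21.78 | 36.00 |
| 4 | 79 | 92 | 13 | 13.00 | 13.00 |
| 5 | 47 | 72 | 25 | 20.16 | 31.00 |
| 6 | 52 | 88 | 36 | 29.45 | 44.01 |
| 7 | 97 | 99 | 2 | 2.00 | 2.00 |
| 8 | 87 | 96 | 9 | 5.40 | 15.00 |
| 9 | 97 | 97 | 0 | 0.00 | n/a |
| 10 | 98 | 99 | 1 | 1.00 | 1.00 |
| 11 | 88 | 94 | 6 | 3.00 | 12.00 |
| 12 | 94 | 92 | -2 | 0.33 | 12.12 |
| 13 | 92 | 98 | 6 | 4.50 | 8.00 |
| 14 | 68 | 81 | 13 | 5.83 | 28.99 |
| **Sum** | **1078** | **1223** | **145** | | |

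**Step 3. Rule out damaged tables.** Several tables lost rows or columns in extraction, so the margins need a second source. The pre sum equals the reported pre total exactly. The net changes fit the printed chi2 values: every ratio is a whole number within the rounding of chi2 (for Question 12, 4/12 = 0.33). The two items with chi2 of 0.00 have net change 0. For Question 1, 56 were correct both times and 69 each time, so 13 moved each way. Hence 1078 + 145 = 1223 does not depend on reading the post-test margins alone.

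**Step 4. Size and pattern of the gap.** 1223 - 1154 = 69. Only Question 1 has a post-test correct count of 69. The post maximum is 13 and the pre maximum 14, as expected if the post total covers 13 items and the pre total 14.

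**Step 5. Effect on the reported gain.**

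- Question 1 in both totals: (1223 - 1078)/100 = 1.45.
- Question 1 in neither: pre 1078 - 69 = 1009, post 1154, (1154 - 1009)/100 = 1.45.
- As reported: 0.76, which is 52% of 1.45.

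**Step 6. Effect on individual changes.** Seven participants scored 14 before. With a post ceiling of 13, all seven must count as declining, out of 25 declines. If Question 1 is the missing item, restoring it adds 1 to the 69 people who had it right afterwards. The 19 declines of one point may then become ties, while the 5 + 1 larger declines remain. The true number of declines lies between 6 and 25; the documents do not fix it. For the same reason, the SD of a corrected change score and the corrected z cannot be recovered from the text.

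**Step 7. Intention.** Change is post minus pre. The protocol lists no pre-test intention items and the SAP says they were asked once, so the pre term is missing for all participants. With only a post proportion q, the change can lie anywhere from q - 1 to q, so for any q strictly between 0 and 1 even its sign is open.

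**The case against.** **The cause is not proven.** True. The documents do not say which items entered the post total. The match to Question 1 and the ceiling of 13 are strong pointers, but only the item data can settle it. The disagreement itself does not depend on the cause.

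**The knowledge result may not need the total.** The item-by-item McNemar tests do not use it, and subgroup comparisons could be made item by item. If one item was dropped for everyone, a difference in mean change between two subgroups shifts only by their difference in the post-test correct rate for Question 1. This stands. It limits the damage to the overall score and what is built on it, but that includes the signed-rank result already reported.

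**A reader might infer that the significant overall gain is unsafe or overturned.** The documents do not support that. If Question 1 was omitted, restoring it leaves each person's change the same or one point higher, and the mean gain rises. The reported figure then understates the gain.

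**On intention, the SAP is open.** It says the items were not analysed and why, and claims no change. Section 4 is worded as a wish, and the question stated at the end of Protocol Section 2 covers knowledge only. All of this stands and makes the point minor. A reader might infer that Section 2 itself promises a pre-to-post intention comparison, or that the omission was hidden; neither is supported. The survey forms were not available, so it cannot be excluded that a one-time item asks people to report a change themselves. That would still not give a pre-to-post difference. The available text stops at the Intent heading, so a descriptive display may already exist.

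**Conclusion.** The reported post-test total is inconsistent with the SAP's own item tables by 69 correct answers, or 0.69 on the mean (12.23 against 11.54). The mean gain should read 1.45 if the item tables are right, against 0.76 as reported. This assumes that the printed margins are correct, which the pre-test match and the McNemar values support, and that the single rule for blanks was applied to both totals, as the SAP states. Omission of Question 1 from the post total only is the likely explanation, not an established one. The existing overall result needs correcting, whether or not subgroups are ever analysed.

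The unexplained absence of the subgroup comparison is a gap against Section 4. The intention point holds only in a narrow form: a pre-to-post difference cannot be computed, this is disclosed, and the link to Section 4 is missing. No intention result has to be withdrawn.

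**What to change.** 1. Re-derive the post-test total from the item data, which Section 4 says have been returned to the site, and check whether Question 1 is included. Score both totals over the same items and state the list.
2. Rerun and restate the signed-rank test, the total-score cross-tabulation, the summary statistics and the post-minus-pre table with its commentary.
3. Use only the corrected total for any comparison of knowledge change by subgroup, labelled exploratory, or state why that comparison was not done.
4. Leave the approved protocol text as it is. Note in the SAP and in any report that the Section 4 analysis of change in intention was not possible for lack of a baseline, and limit conclusions about change to knowledge. Describe intention as a post-education response only, if the SAP's Intent section does not already do so.
5. Restrict the SAP's sentence about identical surveys to the knowledge questions.

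Cost: one recoded variable, a rerun of four existing outputs, a short note and one wording change. At most, one descriptive intention table and one exploratory subgroup table are added. No new data are needed.

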Through this project, NCI/CRCHD intends to answer the following question: Did the colorectal cancer outreach activity change participants' knowledge of colorectal cancer, risk factors, and screening options and recommendations?

3. Study Design

Describe all study procedures, materials, and methods of data collection:

Format and Sites:

NCCC's Community Health Educators ([name] and [name]) will coordinate two to six group education activities/events in New Hampshire and Vermont starting in March 2017. Elements of the group education have been designed by NCI/CRCHD and center around a set of key messages that cover information about colorectal cancer, including incidence, risk factors, prevention, screening recommendations, and screening options (see attached PDF *NCI Colorectal Cancer Outreach and Screening Initiative Toolkit*, pgs. 3-4 and PowerPoint presentation *Screen to Save: Colorectal Cancer Basics*). Where feasible, education may also include information about local options for getting screened for colorectal cancer. Depending on the setting, education will be delivered to participants using one or more of the following educational tools: inflatable colon with educational signage, a PowerPoint presentation, a flipchart/flipbook, written materials/handouts, and verbal instruction. Education will take place in a variety of settings such as community-based organizations (e.g., community businesses, libraries, faith-based organizations, senior centers), fairs and community events, and clinical centers (e.g., health centers, local hospitals). We plan to conduct our first group education activity and data collection effort at the WZID Women's Expo in Manchester, NH on March 11, 2017. Dartmouth-Hitchcock is a sponsor of the event.

Eligible Participants and Data Collection:

Anyone, regardless of age, is welcome and encouraged to participate in the educational activities. However, our research team will be recruiting 100 to 150 people aged 50-74 years old at the time of the event to participate in the evaluation/data collection efforts. At the outreach event, each person recruited will be asked to:

- 1) Review our study information sheet with a CITI-trained research team member

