1. COLORECTAL CANCER STARTS IN WHAT PART OF THE BODY?

Correct Answer: Colon and/or rectum

McNemar's chi2(1) = 0.00 Prob > chi2 = 1.0000

Exact McNemar significance probability = 1.0000

NOT SIGNIFICANT, THERE IS NOT A SIGNIFICANT DIFFERENCE IN THE CORRECT RESPONSES PRE AND POST SURVEY.

Pre Starts in what body part	Post Starts in what body part			Grand Total
	Null	Colon and or rectum	Small Intestine	
Null	2	4	1	7
Colon and or rectum	1	56	10	69
Small Intestine	1	8	10	20
Stomach		1	1	2
Grand Total	4	69	22	100

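### The printed post-test total is 69 correct answers short of the SAP's own item tables, so the mean gain reads 0.76 instead of 1.45; a lesser point is that the planned subgroup comparison is left unaccounted for

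*Protocol*

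**What the plan says.** Under its heading on whether the number of correct answers increased, the SAP tabulates correct answers per participant before and after the intervention, with blanks counted as incorrect. It then says "In order to test of the number of correct responses was significantly different pre and post intervention, the Wilcoxon Signed-Rank Test was used". Nothing there removes an item from either total, and the SAP's background section says both surveys ask the same questions. Item by item, "for each pair of pre and post questions, McNemar's Test was performed". Item 1 is "COLORECTAL CANCER STARTS IN WHAT PART OF THE BODY".

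The SAP's summary statistics print a pre total with mean 10.78 and maximum 14, and a post total with mean 11.54 and maximum 13. The Wilcoxon z is -3.861.

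Protocol section 2 sets the aim: "evaluate the effectiveness of group education about colorectal cancer in changing knowledge and behavioral intention". Section 4 adds: "We will also assess whether there are any differences in changes for audience subgroups (e.g., men/women, age groups, participants at different events". It names no test, cut points or sample size for this. The SAP gives a reason for not analysing intent but does not mention subgroups.

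**The concern.** A 14-item score that reaches 14 before the education and never exceeds 13 after it suggests that the two totals count different items. If so, the change score subtracts a 14-item total from a 13-item one. The mean gain, its SD, the table of changes and the Wilcoxon test would all be wrong as printed, and strong scorers would be pushed towards apparent losses.

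Any later subgroup table would inherit the fault, because each group's change would be lowered by its own post-test success rate on item 1. On the subgroup intention itself, a reader cannot tell whether the comparison was dropped, was not feasible, or was done and not reported.

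**Working it through.** **Inputs.** Correct counts per item come from the margins of the 14 item cross-tabs in the SAP. Totals come from its cross-tab of total correct answers, its summary statistics and its table of post-minus-pre changes. Some item tables are damaged in extraction, so I checked the counts against the printed tests with chi2 = (gains - losses)² / (gains + losses). Item 3 gives (32 - 4)²/36 = 21.78, item 6 gives (40 - 4)²/44 = 29.45, and item 1 has 13 gains and 13 losses, giving 0. All 14 chi2 and exact p-values reproduce.

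**The plan's own total-score figures.** I rebuilt the total cross-tab cell by cell, reading the record labelled Yes as a score of 1. It returns both printed means and SDs (10.78 and 2.195; 11.54 and 1.720) and every frequency in the change table. The Wilcoxon statistic follows: (3522 - 2420)/√81481.63 = 1102/285.45 = 3.861 in absolute value. The printed Wilcoxon test was therefore run on the printed post total.

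**Item sums against totals.**
- Pre: 69+66+44+79+47+52+97+87+97+98+88+94+92+68 = 1,078, and 1,078/100 = 10.78, as printed.
- Post: 69+74+72+92+72+88+99+96+97+99+94+92+98+81 = 1,223, and 1,223/100 = 12.23. Printed: 11.54, that is 1,154.
- Shortfall: 1,223 - 1,154 = 69. Item 1 is the only item with 69 correct at post-test.

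**Mean gain.** Printed: 11.54 - 10.78 = 0.76. From the item tables: (1,223 - 1,078)/100 = 1.45. Removing item 1 from both totals gives the same gain: (1,078 - 69)/100 = 10.09, and 11.54 - 10.09 = 1.45.

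**Wilcoxon test after correction.** The 69 answers cannot be assigned to individuals from the tables. I added one point to 69 people and searched over who they might be. This gave |z| from 5.79 to 7.55 and an SD of change from 1.43 to 2.11 (1.75 as printed).

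**The seven people with 14 at pre-test.** The cross-tab shows five moving to 13, one to 12 and one to 10. Restoring item 1 adds at most one point each. Up to five declines may vanish; the other two remain, as at best 14 to 13 and 14 to 11.

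**What a subgroup comparison could detect.** With 80% power and two-sided 5%, the detectable difference in mean change is 2.802 × SD × √(1/n1 + 1/n2). The splits are assumed, because the documents give none.
- 50/50: 2.802 × (1.43 to 2.11) × 0.20 = 0.80 to 1.18 items.
- 80/20: 2.802 × (1.43 to 2.11) × 0.25 = 1.00 to 1.47 items.

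An uneven sex split is plausible, since the protocol plans its first "data collection effort at the WZID Women's Expo in Manchester, NH on March 11, 2017".

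**The case against.** The omission of item 1 is inferred; the SAP does not state it. That stands, and only the scoring code can settle the cause. The mismatch of 69 does not depend on the inference.

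The corrected result points the same way and is stronger, so one may ask why it matters. A reader might infer that the printed claim of improvement fails. It does not. What is wrong is the size of the gain and the picture for high scorers. Nor does the fault reach every pooled test: the McNemar tests work item by item, include item 1 and never use the total. It would also be too much to call all seven declines from 14 artefacts.

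On subgroups, the case against is stronger. The sentence is a loosely worded intention with examples only. Protocol section 3 says no local analysis is planned, while section 4 plans one. Section 4 also refers to an attachment on analysis that is not shown, and the visible SAP ends at a bare heading on intent. A reader might suspect that the comparison was run and withheld; nothing in the documents supports that.

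It is also tempting to argue that change must be adjusted for pre score. In the printed data, people with 10 or fewer correct at pre-test gained 1.78 on average (n=41) and those with 13 or 14 lost 1.05 (n=19). But those groups are picked on the observed pre score, so regression to the mean contributes, and the figures carry the scoring fault. Sex, age and event groups are not formed that way. Adjustment can itself mislead: if two groups start 1 item apart and gain equally, and post score rises 0.50 per pre-test item (0.49 in the printed data), raw change differs by 0 but the adjusted difference is 1 - 0.50 × 1 = 0.50.

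**Conclusion.** Wrong as written. The printed post total contradicts the SAP's own definition and item tables by 69 answers, and the mean gain is about half of what those tables imply (0.76 against 1.45). This rests on the item counts, which reproduce every printed McNemar result. That item 1 is the cause is very likely but unconfirmed. The total-score summaries, the total cross-tab, the change table and the Wilcoxon test need correcting. The conclusion that knowledge scores rose does not change.

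The missing subgroup comparison is a minor, unexplained departure from protocol section 4, judged on visible text only. With 100 people, only differences of roughly 0.8 to 1.5 items would be detectable at the assumed splits, so an unremarkable subgroup table could not show that an audience gained nothing.

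**What to change.** 1. Check the scoring code. Rescore the post total on all 14 items, or drop item 1 from both totals. Check the record labelled Yes in both totals, which fits the printed means only as a score of 1. Reissue the total cross-tab, means, SDs, change table and Wilcoxon test.
2. After the rescore, choose one of two courses. One is to state in the SAP that the subgroup comparison was not done and why. The other is to add one table, labelled exploratory, with n, baseline mean and mean change with 95% CI by sex and by age group (cut points stated), and by event if it can be recovered. The main contrast should be the between-group difference in change, since that is what the protocol asks about, with the model adjusted for pre score as a sensitivity analysis only. Note the ceiling (items 7, 9 and 10 were 97 to 98% correct at pre-test, and 32 of 100 people sit at the printed post maximum), the limits of baseline adjustment in non-randomised groups, and the detectable difference for the actual splits.
3. Reconcile protocol sections 3 and 4 on whether a local analysis is planned.

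The cost is one rescore, plus one sentence or one small table with wide intervals. Three independent tests at 5% would carry a 1 - 0.95³ = 14% chance of at least one false positive. I assume the pre-test demographics include sex and age, as the form is not shown. Event may not be recoverable: the participant ID holds site and region codes, and "the last 3 digits will be sequentially assigned to participants".
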